7 MEASUREMENT OF STUDY ENDPOINTS

Uptake of genetic testing will be measured as the proportion of participants proceeding to genetic testing following delivery of pre-test information either digitally, or via a telephone consultation with a genetic counsellor.

Knowledge will be assessed using a study-specific questionnaire, designed to test knowledge in key areas of genetic susceptibility awareness for breast/ovarian cancer. The questionnaire has been (i) developed using two previously published questionnaires developed to evaluate knowledge following delivery of genetic counselling information about increased risk for breast cancer, (ii) tested on 3 clinical genetics professionals, 3 oncologists, and (iii) reviewed by our PPI panel comprising patients with breast cancer and patients who have undergone BRCA-testing^{40, 54}.

Anxiety will be measured using the Spielberger state-trait anxiety inventory⁵⁵ and the short form Intolerance of Uncertainty scale⁵⁶.

The Spielberger state-trait anxiety inventory consists of two self-administered, 20-item questionnaires, with each item rated on a four-point Likert scale. It assesses anxiety proneness (trait) and the current state of anxiety change (state). The Trait anxiety is measured only once and the State at each time point. High STAI scores signify greater anxiety.

Research suggests that intolerance of uncertainty may be very important in understanding worry and may play a key role in the etiology and maintenance of worry. Evidence for the connection between intolerance of uncertainty and worry comes from studies that established that worriers possess a number of characteristics that set them apart from non-worriers. For example, worriers have been

shown to require more information before arriving at a decision ⁵⁷. The need for additional information may be a means for lowering the level of uncertainty.

Decline on account of lack of access to digital interface will be assessed from completed anonymous study summary forms posted into the secure study hub drop boxes.

'Test-offer-to-results' time (study compared to audit of timings under current pathways at participating centres)

Helpline usage will be assessed from a central log of the number, content and duration of calls made to the genetic counsellor telephone hot line.

Healthcare professional satisfaction will be assessed using a study specific survey

Patient satisfaction will be measured using a digital study specific survey.

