8.4 Consent to proceed to genetic testing

- For both arms, if a participant decides to proceed with the genetic test they will sign a digital 'BRCA-test consent' form, which will be formatted to BSGM (British Society of Genomic Medicine) standards. All participants will receive a copy of their signed BRCA-test consent form via secure email/post.
- The participant will have two days following test-consent to reverse the decision to proceed with the BRCA-test. Beyond those two days, the test will proceed.
- If a signed 'BRCA-test consent' form is not received from a participant, the BRCA-DIRECT study system will send three reminders 1, 2 and 3 days after the participant viewed the digital pre-test information or had a telephone consultation with a genetic counsellor.
- If signed consent is not received after 8 weeks, the temporarily stored sample and Expression of Interest form will be destroyed and the participant will be withdrawn from the study.
- If a participant subsequently decides to proceed to genetic testing during the active period of the study, and is willing to provide another saliva/blood sample, this will be discussed with the patient and a test conducted if feasible.

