8.9.1 Schedule of patient reported outcome assessments

| Time point | STAI Trait (Y-2) | STAI State (Y-1) | Intolerance of Uncertainty | Knowledge Score | Participant Satisfaction Survey (+ optional telephone interview) |
|---|------------------|------------------|----------------------------|-----------------|--|
| T0 - Baseline | ✓ | ✓ | ✓ | ✓ | |
| T1 – 24 hours after giving consent for genetic test to proceed | | ✓ | | ✓ | |
| T2 – 7 days after notification that test results are available | | ✓ | | | ✓ |
| T3 – 28 days after notification that test results are available | | ✓ | | ✓ | ✓ (reminder if not done at T2) |

All calls to the telephone hotline will be logged on BRCA-DIRECT system by the genetic counsellor who took the call (content and duration of call).

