12.1 Sample size and power calculation for measurement of study endpoints

Sample size

To ensure >95% likelihood of identifying ≥ 5 individuals with a pathogenic_variant at each of the two recruitment sites (prevalence in unselected breast cancer of BRCA pathogenic_variants is $\sim 2\text{-}3\%$) and to test thoroughly the respective pathway logistics as shown below:

- Digital pre-test information – genetic test – digital notification of results
- Digital pre-test information - genetic test – notification of results from genetic counsellor
- Pre-test information from genetic counsellor – genetic test – digital notification of results
- Pre-test information from genetic counsellor – genetic test – notification of results from genetic counsellor

Recruiting 500 cases per site would give 97% probability to detect ≥ 5 individuals with a pathogenic_variant per site (assuming, conservatively, the frequency of BRCA pathogenicity is 2%).

Power calculation for measurement of study endpoints

The table below illustrates the non-inferiority margin in the patient reported outcome measures we would predict on one-sided analysis for non-inferiority of BRCA-DIRECT against standard pathway.

| | Attrition | Predicted available participants (following attrition) | Assumptions (reference *) | Power | Sample size required for 80% power (digital: clinician = 1:1) | Significance level (one-sided) | Non-inferiority margin | Notes |
|----------------------|-----------|--|--------------------------------|-------------------------------|---|--------------------------------|------------------------|--|
| Test uptake | 0% | 1000 | 90% test uptake in both groups | 80-85% with 1000 participants | 934 | 0.025 | 5.5% | Calculated using http://www.hwasoon.kim/NISSC/#!/binary |
| STAI state T1 | 0% | 1000 | Mean 43.2, SD 13.5 (*58) | 90-95% with 1000 participants | 636 | 0.025 | 3 | Calculated using http://www.hwasoon.kim/NISSC/#!/continuous |
| STAI state T2 | 10% | 900 | Mean 43.2, SD 13.5 (*58) | 90-95% with 900 participants | 636 | 0.025 | 3 | |
| STAI state T3 | 20% | 800 | Mean 43.2, SD 13.5 (*58) | 85-90% with 800 participants | 636 | 0.025 | 3 | |
| Patient satisfaction | 20% | 800 | Mean 3.75, SD 1 (*59) | 90-95% with 800 participants | 56 | 0.025 | 0.75 | |
| Knowledge score T1 | 20% | 800 | Mean 5.71, SD 1.55 (*36) | >95% with 800 participants | 38 | 0.025 | 1.40 | |

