12.4 Statistical analysis

During this study and its internal pilot on the first 60 women randomised to each arm, we shall monitor closely and evaluate time taken for data collection, processing and analysis.

The progress of participants through the trial will be shown in a CONSORT⁶⁰ flowchart. Summary statistics will be calculated by trial group at baseline and at each follow-up time point. Normally distributed variables will be described by their means and standard deviations, skewed continuous variables by their medians and interquartile ranges and categorical variables by frequencies and percentages. The primary analysis will be on the per protocol population but we will also perform an analysis of complete cases following intention to treat principles. Further, we may use multiple imputation methods for quantitative outcome measures such as STAI, Patient satisfaction and Knowledge scores.

Continuous outcomes will be analysed using linear mixed effects models with fixed effects for baseline measure of outcome, randomisation arm, centre and time point, with a random effect for participant. Binary outcomes will be analysed using mixed effects logistic regression models with the same set of fixed/random effects. Other baseline covariates considered a priori to be prognostic of outcome may be included in these models. We will report two-sided 95% confidence intervals for each outcome comparison between the arms, with the main focus on comparison of the lower 95% confidence limit and the margin for non-inferiority. A full statistical analysis plan will be written and signed off prior to data analysis. Analyses will be conducted in Stata version 17.0⁶¹ or higher.

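### The mixed logistic model set for binary outcomes does not fit the primary endpoint, and nothing links it to the absolute 5.5-point margin

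*Combined protocol and SAP*

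**What the plan says.** Section 12.4 specifies, for continuous outcomes, "linear mixed effects models with fixed effects for baseline measure of outcome, randomisation arm, centre and time point, with a random effect for participant". It then says "Binary outcomes will be analysed using mixed effects logistic regression models with the same set of fixed/random effects" and makes no exception for the primary endpoint. The decision is to focus on "comparison of the lower 95% confidence limit and the margin for non-inferiority", using two-sided 95% intervals, and "The primary analysis will be on the per protocol population", with a complete-case intention-to-treat analysis as well. A full analysis plan is promised before data analysis; it is not part of the document reviewed.

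Section 7 defines the primary endpoint: "Uptake of genetic testing will be measured as the proportion of participants proceeding to genetic testing following delivery of pre-test information". Section 8.4 shows how it arises: "if a participant decides to proceed with the genetic test they will sign a digital" consent form, reversible for two days. Uptake is not in the repeated-assessment schedule of section 8.9.1, whose first follow-up (T1) is itself timed "24 hours after giving consent for genetic test to proceed".

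In section 12.1 the test-uptake row assumes 90% uptake in both groups and no attrition. Its power, required total, one-sided significance level and margin (in per cent) read "80-85% with 1000 participants | 934 | 0.025 | 5.5".

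**The concern.** Uptake is the only clearly binary outcome that the plan compares between the randomised arms. Decline for lack of digital access is recorded before randomisation, helpline use is a proportion within the digital arm, and anxiety, satisfaction and knowledge are planned as means. The sentence on binary outcomes therefore cannot be set aside as general wording meant for something else.

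Two things are wrong with it for uptake. First, the model was built for repeated measurements, and uptake is measured once. Second, a non-inferiority decision needs the confidence limit and the margin on the same scale. A logistic model gives an odds ratio, the margin is a difference in percentage points, and the plan has neither an odds-ratio margin nor a conversion. If an odds ratio were reported, it could not be judged against the stated margin. If the participant term were kept, that odds ratio would also depend on a variance that the data hardly inform.

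**Working it through.** **1. The plan's own figures and the scale of the margin.** Inputs from section 12.1: 90% uptake in both arms, margin 5.5%, one-sided 0.025, 80% power, 1:1 allocation.

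- Absolute margin: n per arm = (a + b)² × 2 × 0.9 × 0.1 ÷ 0.055², with normal quantiles a = 1.96 and b = 0.8416. The result is 467.04, which gives the stated 934 (2 × 467). Power at 500 per arm = Φ(0.055/√(0.18/500) − 1.96) = 82.6%, inside the stated 80-85%.
- Relative margin: 0.055 × 0.9 = 0.0495. Then n per arm = 576.6, or 1154 in total, and power at 500 per arm = 74.2%. Neither matches.

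So the margin is 5.5 absolute percentage points, although the document does not print that word.

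**2. The five model terms, applied to uptake.**

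- Arm and centre: applicable.
- Baseline measure of outcome: none exists. Section 4.2 excludes women already tested, so any baseline value would be constant.
- Time point: one occasion only, so nothing to estimate.
- Participant random effect: with a single binary record per woman, the data inform only the marginal probability in each arm-by-centre cell. The random intercept merely changes the shape of the link, so its variance is practically not identifiable.

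**3. What the participant term does to the result.** Illustration with assumed counts: in the control arm, 225 of 250 women at each of the two sites; in the digital arm, 222 of 250 at one site and 223 of 250 at the other. The arm totals are 450 and 445 of 500. Arm and centre are in the model, the participant SD is fixed in turn, and the likelihood is computed by Gauss-Hermite quadrature. The log-likelihood at SD 0 is -335.79; the table gives its fall from there in units of 0.00001.

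| Participant SD | Fall in log-likelihood | Odds ratio | Lower 95% limit | Standardised difference (95% CI) |
|---|---|---|---|---|
| 0 | none | 0.899 | 0.600 | -1.0 point (-4.8 to +2.8) |
| 1 | 3 units | 0.889 | 0.568 | same |
| 2 | 6 units | 0.861 | 0.486 | same |
| 3 | 7 units | 0.824 | 0.395 | same |

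The likelihood is flat, the odds ratio drifts, and the difference in uptake does not move. With a strongly uneven assumed split by site (control arm 235 of 250 and 215 of 250; digital arm 233 of 250 and 212 of 250) the log-likelihood changes by only 0.002, the odds ratio goes from 0.897 to 0.819, and the difference from -1.00 to -1.01 points.

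**4. Whether the scale can matter.** The plan gives no odds-ratio margin. If someone converted 5.5 points at the planned 90% uptake, it would be the odds at 84.5% uptake (5.45) divided by the odds at 90% uptake (9), which is 0.606. In the illustration the difference clears its margin (-4.8 is above -5.5), but the ordinary logistic lower limit of 0.600 falls just below 0.606. The converted margin also depends on control uptake: 0.684 at 85% and 0.449 at 95%. This conversion is an assumption made here only to show that the choice of scale is not neutral.

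**5. Check of the proposed analysis.** Simulation assuming 500 women per site, logistic regression standardised to the difference, delta-method interval. Power at 90% versus 90% is 83.2% with arm and centre, and 83.6% with one added prognostic covariate of assumed log-odds 0.5 per SD (10,000 runs each). The false non-inferiority rate at 84.5% versus 90% is 2.6% and 2.5% (40,000 runs each).

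**The case against.** The strongest reply is that the intended scale can be recovered. Uptake is defined as a proportion, the only margin for it is 5.5% against a 90% proportion, and comparing a confidence limit with that margin implies a difference in proportions. Section 12.4 mentions no odds ratio. A protocol often leaves post-estimation steps to the analysis plan, and one is promised. On this view the unsuitable terms have no consequence: baseline and time point are constants and drop out, software may shrink the participant variance to zero, and step 3 itself shows that the standardised difference hardly moves. The odds-ratio drift comes from assumed counts and from SDs of up to 3 that no document figure supports.

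Much of this stands. The scale can be inferred, the illustration shows non-identifiability rather than an expected error, and the separate plan may close the gap. What remains is that the only model stated for the sole primary endpoint does not suit it, and that the step which would make it harmless is not written down. Shrinking the variance to zero would still leave an odds ratio without a margin. Marginal standardisation is also not the only valid route; a site-stratified risk difference would serve.

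**Conclusion.** The concern holds. As written, section 12.4 applies a repeated-measures logistic model to an endpoint measured once per woman, and it names no effect measure or step that brings the result onto the scale of the margin. The stated sample size and power are correct and unaffected. The consequence is conditional: if the fit is standardised to the difference in uptake, the conclusion is practically the same whatever happens to the participant term; if an odds ratio is reported, it cannot be set against the stated margin. Reading the margin as absolute rests on its reproducing 934 and 80-85% power. The size of the odds-ratio drift rests on assumed counts and SDs. The point should be fixed before analysis; it is not evidence that the final analysis was wrong.

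**What to change.** Add one paragraph to section 12.4, repeated in the analysis plan, along these lines:

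> Uptake will be analysed by single-level logistic regression with arm and centre, plus any baseline covariates named in advance; the baseline-outcome, time-point and participant terms are omitted. The fit will be marginally standardised to the absolute difference in uptake (digital minus telephone) with a two-sided 95% confidence interval. Non-inferiority is declared if the lower limit lies above -5.5 percentage points.

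The populations stay as section 12.4 has them: per protocol is primary, with the complete-case intention-to-treat analysis alongside. The paragraph should say so, to avoid being read as requiring success in both. Keep the mixed logistic model only for binary outcomes measured repeatedly, if there are any. The cost is this one paragraph: no new data and no change in sample size.

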13 DEVELOPMENT OF THE BRCA-DIRECT DIGITAL SYSTEM

The BRCA-DIRECT study databases and user-interface will be developed prior to recruitment with inbuilt user testing during development.

User interfaces required are:

- Participants
- Genetic counsellors
- Pathology lab
- Study coordination team

Functionality requirements are:

- Login/access at any time
- Withdrawal option available at any time
- Data entry
- Provision of digital pre-test information
- Digital consent form completion and signature
- Calendar management
- Saliva/blood sample management
- Automated reminders for uncompleted actions
- Automated messages linked to actions
- Production of test results letters
- Production of reports
- Participant pathway management to prevent deviations from protocol
- Notification/alerts of participant enrolment, non-compliance and withdrawals
- Communication between research team
- View and download key data including digital consent forms

[figure not shown]
Additional requirements:

- 1:1 randomisation to pre-test information delivery method
- Selective randomisation of BRCA negative participants to receive results from a genetic counsellor

During development, the system will be user tested to ensure correct functionality. Previous breast cancer patients will provide PPI review of the 'look and feel' of the system, and its ease of use.

Further evaluation will take place during the 'pause' after 120 participants have been enrolled in case any major unanticipated user problems are identified. These will be resolved before recruitment re-commences.

BRCA-Direct Data Flow Diagram

14 STANDARD NHS GENETIC TEST FOR BRCA1/BRCA2/PALB2

Genetic Testing will be delivered by the NHS North Thames Genomic Laboratory Hub NIHR Biomedical Research Centre for Molecular Pathology (**ICR/RMH CMP**), located at the Royal Marsden Hospital, Surrey. The ICR/RMH CMP is a NeQAS-approved, ISO 15189 accredited medical diagnostic molecular genetics laboratory. Sample handling, sequencing and reporting will be performed to NHS diagnostic standard.

Saliva/blood samples will be supplied by participants at the Royal Marsden Hospitals (RMH) and Manchester Foundation Trust (MFT) NHS Hospitals, and will be identified via four patient identifiers marked on the tube (first name, surname, DOB, postcode). Samples collected at MFT will be transferred to the ICR/RMH CMP and will be stored and managed in accordance with established standards for NHS diagnostic patient samples. Transfer of saliva/blood samples will comply with biological sample transfer guidelines of the European Agreement concerning the International Carriage of Dangerous Goods by Road (ADR).

The request for a BRCA test will be initiated by the BRCA-DIRECT study databases 48 hours after a participant has given digital consent for genetic testing to proceed. The request will contain a unique study patient identifier (PIN), first name, surname, DOB, postcode and hospital number and will be transferred securely to the LIMS (Laboratory Information Management System) at ICR/RMH CMP. The genomic result and interpretation will then be returned from the CMP LIMS to the secure BRCA-DIRECT study databases via a secure upload.

DNA will be extracted from the saliva/blood samples and quantified via Qubit. Targeted libraries will be created via Qiaseq library preparation with DDR capture Panel hybridisation and enrichment comprising all coding exons and intron-exon boundaries of *BRCA1/BRCA2/PALB2*, and sequencing will be performed to NHS diagnostic test standards (minimum median coverage 50x, minimum per-base coverage 25x, with bidirectional reads). Data processing and calling of sequence variants and exon-level aberrations of dosage will be undertaken using established analytical pipelines and variant interpretation/classification using ACMG standards. The test results will be as valid as any other generated in the NHS and will therefore be valid for NHS clinical use.

Following the test, unused saliva/blood sample will be destroyed. Extracted DNA will be stored securely at the ICR/RMH CMP for an indefinite period of time.

If digital consent is not received from a participant, or a request to destroy a sample is made by the local site or participant, the sample will be destroyed in a manner appropriate for biological waste according to ICR guidelines and a record kept of this destruction.

15 DATA HANDLING AND RECORD KEEPING

15.1 Data acquisition

Data will be entered via the BRCA-DIRECT interface onto the BRCA-DIRECT data storage system.

Each participant will be assigned a unique participant identifier (PIN) and all of their data will be stored under this PIN.

Data will be entered by the following persons:

- Participant – family history, questionnaires, consent for genetic testing to proceed, user feedback survey
- Local site genetic counsellor – baseline data (including patient identifiable data), sample receipt, sample transfer, telephone hotline usage, record of consultations conducted
- ICR/RMH CMP - sample receipt, test results, record of destruction (unprocessed samples)

This data storage system will be comprised of two databases. The first database will handle PID. This will be partitioned and linked via PIN to the second, which will be PID-free, serving an operational purpose for the interface. These databases will meet all data security standards and be held within the ICR.

15.2 Data quality

Electronic participant questionnaires will be designed to constrain answers that can be supplied (range checks) and to prevent submission of incomplete forms. Computerised and manual consistency checks will be performed on a regular basis via downloads/reports from the study databases.

Newly entered family history questionnaires will be checked by the local site genetic counsellor and queries issued in case of inconsistencies.

The ICR/RMH CMP utilises a secure Line Information Management System (LIMS) by which the PID and genetic data generated are stored and QC (quality control) checks are implemented as routine. Sample handling, sequencing and reporting will be performed to NHS diagnostic standard.

15.3 Data access

Access to the central study databases will be limited according to user type. The restrictions will be built into the system as it is developed.

Access to the BRCA-DIRECT interface by the participant will require a login process. This will allow the participants journey through the study material to be mapped, and help authorise that all digital consenting and questionnaires are completed by the intended person.

